#### 8.3.3 MULTIPLICITY ADJUSTMENT

The key secondary endpoint will only be formally tested if statistical significance has been obtained for the primary endpoint.

This step-down procedure ensures that there will be strong control of the experiment-wise type 1 error across the primary endpoint and the key secondary endpoint.

If the primary endpoint is found to be non-significant, the key secondary endpoint will still be analysed but a footnote will be added to all related tables for the key secondary endpoint stating that p-values and confidence intervals are to be viewed as descriptive.

#### 8.4. SECONDARY QUALITATIVE MEASURES

The COVID-19 related assessments, which are secondary qualitative measures, will be summarised for the Day 5, 8 and 14 Visits.

The following will be tabulated for the FAS:

- Loss of taste (yes/no), both overall and separately among subjects who recorded loss of taste at baseline
- Loss of smell (yes/no), both overall and separately among subjects who recorded loss of smell at baseline
- In the past 24 hours, have you returned to your usual health (before your COVID-19 illness)? (yes/no)
- In the past 24 hours, have you returned to your usual activities (before your COVID-19 illness)? (yes/no)

A listing will also be provided for the COVID-19 related assessments.

# 8.5. SAFETY ENDPOINTS

The safety endpoints will be summarised (i.e. listed and/or tabulated) for the safety population.

#### 8.5.1. EXPOSURE

'Exposure' is defined as the number of COVID-19 treatments (out of the 14 scheduled) that an individual undergoes during their time on the study.

This information will be tabulated as both a continuous and categorical variable (categories: 0,1,2,3,4,5,6,7,8,9,10,11,12,13,14).

A listing will also be produced which provides information on the Day number and time that each treatment is taken, with a flag to indicate if the treatment was given in Clinic, a yes/no variable for whether the subject discontinued treatment due to an TEAE/TESAE, the coded TEAE term for subjects with Yes (for discontinued treatment due to an TEAE or TESAE), the day number that treatment was discontinued (where applicable), a yes/no variable for whether the subject discontinued the study, the reason (that trial subject discontinued the study) for subjects with Yes, the day number that the subject discontinued the study.

#### 8.5.2. CONCOMITANT MEDICATIONS AND THERAPIES

Concomitant medications and therapies will be defined as medications and therapies begun after first treatment, and they will be summarised for the safety population.

Note: Medication/therapy detailed information comes from associated 'Medication' and 'Therapy' CRFs. WHODrug coding information comes from an associated 'WHOdrug coding' CRF.

The following information will be listed:

- Was the medication/therapy prescribed during the study (yes, no)
- Category (head, ears, eyes, nose, throat, mouth, cardiovascular system, lungs, pancreas, kidney, urological system, nervous system, blood, lymph nodes, endocrine system, musculoskeletal system, skin, genital/reproductive tract, allergies, cancer, immunodeficiency, psychiatric illness, substance abuse, autoimmune disease, other)
- Start date/Stop date (stop date can be 'ongoing')
- Reason for use (COVID-19 symptoms, chronic disease/medical history, adverse even, other)
- Indication (if therapy only)
- o Dose
- o Dose unit (capsule, drop, ...)
- o Dose form (aerosol, capsule, ...)
- o Frequency (once, twice weekly, ...)
- o Generic drug name and drug code
- WHOdrug product name
- o Preferred name

- o ATC text
- Start date/End date (End date can be 'ongoing')

In addition, the same listing will be produced but restricted to concomitant medications that are given for COVID-19 related symptoms.

A table will be produced listing counts of the different types of concomitant medications/therapies (only those taken after initiating treatment) in each of the ATC highest level classification groups along with whether or not the individual medication was prescribed during the study (yes/no).

In addition, the same table will be produced but restricting those concomitant medications to those given for COVID-19 related symptoms.

Since the CRF does not identify which medications and therapies were given for COVID-19 related symptoms, the sponsor will provide Quantics with a separate data set with a flag indicating which medications and therapies to which this applies.

### 8.5.3. Adverse Events

All adverse event (AE) tables will be produced for the Safety population, and will be presented by treatment group. The AE incidence tables will all be based on treatmentemergent adverse events (TEAEs), but all listing-type tables and the AE data listing will also include non-treatment-emergent AEs. A TEAE is defined to be an AE which starts after initiation of treatment, or a medical condition which was present prior to initiating treatment but which increases in severity after starting treatment. TEAEs will be captured and identified by the investigator who will assess the increase in severity part of the TEAE definition by comparing post-baseline Medical History/Physical Examination with baseline Medical History/Physical Examination. The only possible non-TEAEs recorded could be those AEs experienced between signing the ICF and the time of the first treatment, but as this time period is very short it is expected that there will be very few if any AEs that are not TEAEs. All AEs will be coded using MedDRA version 23.0 or higher.

The following 12 incidence tables will be produced for TEAEs which for #2-#8 will be sorted by system organ class (SOC) and preferred term (PT):

- 1. Overall TEAE summary table (with counts for #2-#12)
- 2. TEAE incidence table
- 3. Treatment-emergent SAE (TESAE) incidence table (including a separate count for any deaths)
- 4. TEAE incidence table by severity
- 5. Device-Related TEAE (DR-TEAE) incidence table
- 6. DR-TEAE incidence table by severity
- 7. Anticipated DR-TEAE incidence table
- 8. Unanticipated DR-TEAE incidence table overall and by severity
- 9. Solicited TEAEs incidence table overall and by severity
- 10. Solicited DR-TEAEs incidence table overall and by severity
- 11. TEAEs leading to discontinuation of treatment incidence table

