8.4 Procedures for Clinically Significant Findings

If in the judgement of the PI any finding poses a previously unknown risk to an individual or leads to a diagnosis of a disease or condition that would have disqualified the individual for enrollment, the study subject will be withdrawn from the study immediately.

All clinically significant findings that occur post randomization and after the first use of the RD-X19 device will be considered TEAEs.

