8.6.4 Treatment Emergent Adverse Event Reporting

Information on all TEAEs should be recorded on the appropriate source document and e-CRF. All clearly related signs, symptoms and results of diagnostic procedures performed because of an TEAE should be grouped together and recorded as a single diagnosis.

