8.6.9 Severity of Treatment Emergent Adverse Events

All TEAEs will be assessed for severity according to the toxicity grading scale of mild, moderate, and severe..

The following guidelines will be used to describe severity:

- Mild (Grade 1): Events that are usually transient and may require only minimal or no treatment or therapeutic intervention and generally do not interfere with the subject's usual activities of daily living.
- Moderate (Grade 2): Events that are usually alleviated with additional specific therapeutic intervention. The event interferes with usual activities of daily living, causing discomfort but poses no significant or permanent risk of harm to the research subject.
- Severe (Grade 3): Events interrupt usual activities of daily living, or significantly affects clinical status, or may require intensive therapeutic intervention. Severe events are usually incapacitating.

TEAEs characterized as intermittent require documentation of onset and duration of each episode. A TEAE is not counted as a separate or new TEAE if at the next clinic visit, the TEAE is persistent at the same of lesser severity level. It shall be recorded as a new TEAE if it worsens in severity. The same TEAE verbatim term with a worsened severity score will be documented as an independent event, including start and stop dates. The start and stop date of each reported TEAE will be recorded on the appropriate e-CRF. All device-related grade ≥ 2 TEAEs (any grade greater than mild is considered unanticipated) will be reported.

See SAE source document for information to be submitted.

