9.4.2 Safety Analyses

Summaries for all safety data will be presented by treatment group based on the Safety population. The number of hospitalizations will be tabulated and full details will be provided in listing form for any such hospitalizations. See section on Reporting Requirements for regulatory reporting of presumed device-related SAEs and patterns of device-related AEs.

A TEAE is defined to be an adverse event (AE) which starts after initiation of treatment, or an AE which was present prior to initiating treatment but which increases in severity after starting treatment, excluding signs and symptoms of COVID-19. Incidence tables by system organ class and preferred term will be produced for AEs, SAEs, TEAEs, device related TEAEs (including separately those that are anticipated and unanticipated, as designated by severity level, and resulting clinical outcomes such as treatment discontinuation/withdrawal), TEAEs that led to discontinuation of treatment, and TEAEs by severity. The details of SAEs and any deaths will also be summarized.

Protocol deviations will be summarized in tabular and listing form.

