## 4.4. SAFETY ENDPOINTS

The safety analysis will consider all TEAEs whether solicited (as part of the reactogenicity assessments including oropharyngeal assessment) or unsolicited.

In addition to TEAEs, the following safety endpoints will be assessed:

- o Concomitant medications and therapies
- o Vital signs
- o Physical examination

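### SAP 8.5.3 lacks the Protocol 9.4.2 exclusion of COVID-19 signs and symptoms from the analysed TEAEs, so the all-cause TEAE totals can include disease course

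*SAP*

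**What the plan says.** Protocol 9.4.2 (Safety Analyses) defines a TEAE as an AE that starts after treatment begins, or one already present that "increases in severity after starting treatment, excluding signs and symptoms of COVID-19". It then asks for separate AE and TEAE tables: "Incidence tables by system organ class and preferred term will be produced for AEs, SAEs, TEAEs, device related TEAEs".

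SAP 8.5.3 (Adverse Events) also has a new-onset limb and a worsening limb. The second reads "a medical condition which was present prior to initiating treatment but which increases in severity after starting treatment", and the sentence ends without the exclusion. All 12 incidence tables rest on this definition. SAP 4.4 is equally broad: "The safety analysis will consider all TEAEs whether solicited" or unsolicited. No other part of the SAP removes COVID-19 signs and symptoms from the TEAE tables.

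Protocol 4.3, 8.6.1 and 12.0 also define a TEAE without the exclusion. Within the protocol it appears only in 9.4.2.

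The SAP's reference list cites Protocol Version 3.0 (2023), while the supplied protocol is Version 3.1 of 7 February 2024. The SAP's later change-control entry, 24 March 2024, postdates Version 3.1 and mentions only primary and key secondary endpoint analyses.

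**The concern.** Inclusion criterion 3 requires at least two moderate or worse COVID-19 signs and symptoms at entry, or one plus fever. The primary endpoint is time to sustained resolution of those symptoms. If the symptoms also enter the AE record, a count of subjects with any TEAE becomes partly a second reading of efficacy. A device that relieves symptoms could then show a lower all-cause TEAE total and so offset a real excess of other events. A device with no benefit would carry disease events in both arms, which dilute the comparison.

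The exclusion in Protocol 9.4.2 keeps the two apart. Followed literally, the SAP does not, and nothing in it marks this as an intended departure. SAP 2.1 describes the document as elaborating the protocol's analysis, so a reader would expect the two definitions to agree.

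**Working it through.** The documents state no figure to reproduce, so the check is a comparison of rules.

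**1. Possible analysed sets.** The exclusion in 9.4.2 follows the worsening limb and could attach to that limb only or to both. With the SAP's rule, that makes three candidate TEAE sets.

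**2. Illustration, with no assumed rates.** Take one subject with cough and no nausea at baseline. After first treatment the investigator records worsened cough and new nausea as two separate AEs, neither device-related.

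| Rule | Cough (worsened) | Nausea (new) | TEAEs | In any-TEAE total |
|---|---|---|---|---|
| SAP 8.5.3 | counted | counted | 2 | yes |
| Protocol 9.4.2, exclusion on worsening limb only | excluded | counted | 1 | yes |
| Protocol 9.4.2, exclusion on both limbs | excluded | excluded | 0 | no |

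The device-related count is 0 under every rule. The protocol's separate AE table holds 2 under every rule.

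Protocol 8.6.4 says that clearly related signs and symptoms "should be grouped together and recorded as a single diagnosis". If the site does so here, the SAP count is 1. The protocol count is then 0 or 1, depending on whether a COVID-19 diagnosis term counts as a sign or symptom. If investigators record no COVID-19 symptoms as AEs, all rules agree.

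**3. Can such events enter the AE record?** Entry is limited. Under SAP 8.5.3 the investigator judges worsening by comparing medical history and physical examination with baseline, not from e-diary scores. It is not prevented:
- the new-onset limb has no such restriction;
- the interim history in Protocol 8.6 asks about symptoms that began after treatment started;
- in EB-P12-01 (31 subjects, Protocol 4.1) every TEAE captured was a COVID-19 sign or symptom appearing or worsening.

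**4. Tables exposed.** These are #2 (all TEAEs), #4 (by severity), #11 (leading to treatment discontinuation) and #12 (leading to study discontinuation): 4 of 12, plus their 4 counts in #1. Table #12 is less exposed because SAP 7.2 lists progression to moderate or severe COVID-19 as its own withdrawal reason. Table #3 (serious events) is not a departure, because 9.4.2 tabulates SAEs separately without the exclusion. Tables #5 to #8 and #10 depend on attribution, and #9 and #10 come from the reactogenicity page.

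**5. What is lost.** The SAP expects very few AEs that are not TEAEs, so its TEAE table is close to the protocol's AE table. The events remain. The filtered TEAE view that 9.4.2 requires is missing.

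**The case against.** The other side has a good case on consequence.

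- **The safety objective is device-related events** (Protocol 4.5, SAP 3.1), and those tables are largely untouched. The safety plan is descriptive, with no hypothesis test. SOC and PT rows in #2 and #4 and the full AE listing would show any COVID-19 terms. This stands, and it is why the point is minor. It does not rescue the any-TEAE totals, which cannot be rebuilt from the rows because one subject may have several terms.
- **Three protocol definitions agree with the SAP, and only one sentence differs.** True. Those three can reasonably serve as collection definitions, although the protocol does not label them so. Section 9.4.2 is the analysis rule, so the SAP must apply it or state why it does not.
- **Flagging needs judgement.** This also stands. The first-in-man reactions and TEAEs in Protocol 4.1 include headache, nausea, fever, chills or sweats, and difficulty swallowing. Most of these overlap the endpoint symptoms.

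A reader might go further in three ways that the documents do not support.

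First, that the SAP removed the exclusion deliberately or by oversight. The SAP cites Version 3.0, which is not available here, so neither can be shown.

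Second, that the collection rules will turn baseline symptoms into TEAEs. Protocol 8.4 says "All clinically significant findings that occur post randomization and after the first use of the RD-X19 device will be considered TEAEs", but it sits under a heading about clinically significant findings, after a rule on previously unknown risks and disqualifying diagnoses. Protocol 8.6.9 says "It shall be recorded as a new TEAE if it worsens in severity", but that governs an event already counted as a TEAE. Neither makes diary symptoms into AEs.

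Third, that disease course will dominate the totals, as it did in EB-P12-01. That result shows only that such recording has happened. The documents do not say that the same definition or collection method applied.

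**Conclusion.** The inconsistency is real. Protocol 9.4.2 excludes COVID-19 signs and symptoms from the analysed TEAEs, and SAP 8.5.3 does not and gives no reason. This holds under either reading of how far the exclusion extends. The conflict is with 9.4.2 alone.

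The consequence is conditional. To the extent that investigators record COVID-19 symptoms as AEs, the totals in #2, #4, #11 and, to a lesser degree, #12, with their counts in #1, mix disease course with safety. No size can be given, because the documents contain no TEAE rates for this trial. If no such symptoms are recorded, the difference is zero.

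It would be wrong to infer that device safety is misjudged or that events are hidden. Device-related and SAE tables are largely unaffected, the pausing and stopping rules do not use all-cause TEAE totals, and every term stays visible in the rows and listings. Severity is low to moderate: worth settling before unblinding, with no bearing on the primary efficacy test.

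**What to change.** Before unblinding, and before the database lock that SAP 2.1 sets as the limit for amendments, revise SAP 8.5.3 as follows.

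- Apply the Protocol 9.4.2 exclusion through a blinded, pre-specified flag on MedDRA coded terms. The SAP already provides for a coded-term list for anticipated device-related events (8.5.3) and a sponsor flag for medications given for COVID-19 symptoms (8.5.2).
- State whether the exclusion covers both limbs of the definition or the worsening limb only.
- State whether it covers a grouped COVID-19 diagnosis term recorded under Protocol 8.6.4.
- Present #2, #4, #11, #12 and their counts in #1 by arm, with and without the flagged terms.
- Keep device-related events in both versions, and leave SAEs, hospitalizations and deaths unrestricted.
- Cite the current protocol version.

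Protocol 4.3, 8.6.1 and 12.0 can stay as they are if they are described as collection definitions.

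The cost is a SAP edit, a second version of four tables and four summary counts, and one blinded review of coded terms. Showing four tables twice goes somewhat beyond 9.4.2, although for #2 the pair comes close to the separate AE and TEAE tables that section requests. The main downside is judgement on terms that could be disease or device: sore throat, headache, nausea, fever, chills or sweats, and difficulty swallowing. The dual display does not remove that judgement, but it makes its effect visible.

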#### 12. TEAEs leading to discontinuation from the study - incidence table

For subjects experiencing the TEAE more than once only the most severe will be counted in the incidence tables.

Anticipated DR-TEAEs are those described in Protocol Section 5.2.1, and are anticipated provided that all of the following applies: (i) occurred post-treatment with severity of mild; (ii) did not lead to discontinuation of treatment; and (iii) did not lead to discontinuation from the study. Anticipated DR-TEAEs will be identified by a pre-specified list of MedDRA coded terms or a listing will be provided to Quantics with an identifying flag for any AEs that correspond to an anticipated DR-TEAE.

Unanticipated DR-TEAEs include those TEAEs reported as device-related and which are not described in Protocol Section 5.2.1. In addition, those TEAEs described in Protocol Section 5.2.1 for which any of the following occurs will also be classified as unanticipated: (i) occurred post-treatment with severity of moderate or severe; (ii) led to discontinuation of treatment; or (iii) led to discontinuation from the study.

Solicited TEAEs are those collected by direct questioning of study subjects and are recorded on the CRF pages for Reactogenicity assessment including oropharyngeal assessment. [Unsolicited TEAEs are those spontaneously reported by the subject and/or in response to an open question from study staff or revealed by observation, physical examination, or other diagnostic procedure.] The incidence tables for solicited TEAEs, as derived from the Reactogenicity CRF page, will summarize:

- Clinical judgement (normal, abnormal not due to device, abnormal due to device)
- Pain (absent, present [overall and separate counts for mild, moderate, severe])
- Erythema at the illumination site (absent, present [overall and separate counts for mild, moderate, severe])
- Edema/induration at the illumination site (absent, present [overall and separate counts for mild, moderate, severe])
- Any other pain, redness, swelling or lesion of the oral mucosa (absent, present [overall and separate counts for mild, moderate, severe])

Subjects experiencing the individual solicited TEAE more than once will be counted in the incidence tables under the most severe category. For "Clinical judgement" here also only the most severe will be counted (where "abnormal due to device" is regarded as the "most severe" for this purpose).

The following listing-type tables will be produced:

- 13. Listing-type table of SAEs
- 14. Listing-type table of Device-Related SAEs

- 15. Listing of all hospitalizations including for COVID-19-related symptoms as determined by Hospitalization being recorded as an action taken in the AE CRF.
- 16. Listing-type table of AEs occurring while patient was hospitalized
- 17. Listing-type table of Deaths
- 18. Listing-type table of AEs leading to treatment discontinuation

In #13-#16 and #18 non-TEAEs, if any, will be flagged.

A full data listing will also be produced for reactogenicity assessment and oropharyngeal assessment including all information from these CRF pages at the Day 1, Day 5, Day 8, and Day 14/Early Termination study visits. Similarly, a full data listing will be produced based on information collected on the AE page, where non-TEAEs, if any, will be flagged.

#### 8.5.4. VITAL SIGNS

As the Baseline, Day 5, Day 8, and Day 14 Clinic Visits vital signs are collected as a value and then classified on the basis of the following two questions:

- Value out of range (yes, no)
- Clinically significant (yes, no)

Some vital signs are scheduled to be collected three times at each timepoint for which an average value is then calculated. If for these vital signs less than three assessments are performed then the average of the values collected is used instead.

Variables tabulated (over the safety population) by visit are:

- Oxygen saturation (%)
- Systolic blood pressure (mmHg)
- Diastolic blood pressure (mmHg)
- Heart rate (beats/min)
- Oral temperature (°F)
- Respiratory rate (breaths/min)
- Note: Oxygen saturation and oral temperature are scheduled to be recorded twice daily for Days 1-14 and the tabulated values for these two vital signs will include (average) values recorded in their diary entries as well as the values recorded at the Clinic Visits.

#### 8.5.5. PHYSICAL EXAMINATION

The following information will be listed and frequencies will be tabulated over the safety population. This is performed only at baseline, the day 14 visit, and Early Termination, and as such will only be summarised at those timepoints.

Unless otherwise indicated, the classes are: normal, abnormalities but no clinical significance, abnormal with clinical significance. Note: If 'abnormal with clinical significance' a free-text explanation is given.

- Assessment performed (yes, no)
- o Skin
- o Head
- o Ears
- o Eyes
- o Nose
- o Throat
- o Neck
- o Lungs
- o Heart
- o Liver
- o Spleen
- o Abdomen
- o Extremities
- o Lymph nodes, axillary and cervical
- o Nervous system

